11.6. Pre-discharge visits

The pre-discharge follow up visit should be done before hospital discharge but no later than 8 days past index ablation procedure, even if the subject has to remain at the hospital for a longer time (e.g. due to an Adverse Event).

The data collection at Pre-Discharge includes:

- Date of visit;
- Rhythm at time of pre-discharge;
- Variations in current medication regimen;
- Reportable Adverse Events, if applicable
- Additional Follow Ups/Procedures, if applicable

11.7. Additional visits

Additional visits before the month 4 follow up may occur per physician decision. If an additional visit should occur, the following information should be collected in the eCRF:

- Visit date;
- Type of visit: in-clinic or phone contact,
- Reportable Adverse Events, if applicable;
- Reason for additional follow up including standard of care, due to adverse event or other.

11.8. Additional procedure

In case an additional procedure occurs during the month 4 follow up period, the data of this procedure will be entered in the 'Additional Procedure' eCRF. In case this additional procedure is an ablation procedure (for the same, or different arrhythmias or for and unsuccessful ablation of the arrhythmia presented at index procedure) for which a different mapping system was used or different mapping and/or therapeutic catheters were used, detailed information about this additional ablation procedure will be entered in the 'Additional Procedure' eCRF:

- The name of the EP physician performing the procedure
- Was the additional ablation procedure performed in the LA?
 - o For additional ablation procedures performed in the LA: Did this additional ablation procedure occur as a result of an unsuccessful or incomplete index procedure?
 - Was this additional ablation procedure performed to treat the same arrhythmia as the one from the index procedure? If no, specify the arrhythmia type
 - Was the Rhythmia HDx mapping system, IntellaMap Orion mapping catheter and IntellaNav MiFi OI ablation catheter used for this additional ablation procedure?
 - If yes, this additional ablation procedure will be considered as the month 3 assessment if the month 3 assessment was not yet performed. This additional ablation procedure must be completed in the month 3 assessment visit. Please refer to Section 11.9-3 for more details.
 - If no, in case a different mapping system was used and/or different mapping and/or therapeutic catheters were used, the subject will have to be withdrawn prior to this additional ablation procedure.
 - Please refer to Section 10.2 for more details.

Any reportable adverse event resulting from additional procedures must be captured on the Adverse Event eCRF.

The additional ablation procedure itself should not be reported as a Serious Adverse Event (SAE), unless associated with subject worsening condition. In this case, the additional ablation procedure should be reported in the Adverse Event eCRF as corrective action of the specific SAE reported for the worsening condition.

Form/Template 90702637 Rev/Ver AH LOCALIZE protocol, document 92142978, Rev/Ver AB Page 39 of 65

Additional procedures will not alter the determination of the primary endpoint (acute procedural success), that will be based on the index procedure.

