10.2. Withdrawal

All subjects enrolled in the clinical study (including those withdrawn from the clinical study or lost to follow-up) shall be accounted for and documented. If a subject withdraws from the clinical investigation, the reason(s) shall be reported. If such withdrawal is due to problems related to study device safety or performance, the investigator shall ask for the subject's permission to follow his/her status/condition outside of the clinical study.

Every effort should be made to retain subject enrollment for the duration of the study. During the informed consent process, subjects should be fully informed of the data collection requirements and duration, and should only be enrolled if willing to fully participate in it.

Reasons for withdrawal may include physician discretion, subject choice to retire consent, lost to follow-up, or death. In the event a subject does decide to withdraw from the study, every effort should be made to obtain full information on any on-going reportable Adverse Events up to the point of withdrawal. Subjects should only be considered lost to follow-up after significant effort has been made to contact the subject. For subjects who are "lost-to-follow-up" the investigator/center should have at least three documented attempts to contact the subject prior to completion of the "End of Study" eCRF. Subject withdrawal and lost to follow-up will be documented on the "End of Study" electronic Case Report Form (eCRF). Additional data may no longer be collected after the point at which a subject has been withdrawn from the study or withdraws his/her consent, for whatever reason.

All open reportable Adverse Events should be closed or documented as chronic. Data collected up to the point of subject withdrawal may be used, unless any local regulations apply which require removal of the data.

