11.1. Data Collection

Each Treatment subject will be followed at index procedure, at pre-discharge visit, at the month 3 assessment and at month 4 follow up. In order to reliably capture subject status at study end, the month 4 follow up has to be scheduled within 120 ± 30 days following the index procedure. If the subject needs to undergo an additional ablation procedure in the LA during the follow up period and the Rhythmia HDx mapping system, the IntellaMap Orion mapping catheter and the IntellaNav MiFi OI ablation catheter were used for this procedure, then this additional ablation procedure will be considered as the month 3 assessment if the month 3 assessment was not yet performed. No Protocol Deviation will have to be completed for a Visit Out Of Window. In case a different mapping system was used and/or different mapping and/or therapeutic catheters will be used for this additional ablation procedure in the LA, the subject will have to be withdrawn prior to this additional ablation procedure.

Table 11.1-1 provides an overview of the data to be collected at each visit.

INDEX PROCEDURE ADDITIONAL VISIT MONTH 3 FOLLOW **MONTH 4 FOLLOW** PRE-DISCHARGE PROCEDURE (if applicable) **UP** (120± 30 days) **ENROLLMENT/** (0-7 days post procedure) ADDITIONAL (90±21 days) (if applicable) (Day 0) **Data Collected** X Informed Consent Inclusion/Exclusion X X Demographic data Medical History X X X* X* X* X* Medication Regimen Mapping and procedure data X X X** X X Patient status Χ X X X X X X X X X **Protocol Deviations** Adverse Event/ Device X X X X X X X Deficiency Reporting***

Table 11.1-1: Data Collection Schedule

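### For a left atrial re-ablation with non-study equipment, the protocol orders withdrawal beforehand, bars data after withdrawal, and still requires the procedure record and its adverse events

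*Combined protocol and SAP*

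**What the plan says.** **Withdrawal.** Section 11.1 covers an additional ablation done with a different mapping system or different catheters: "for this additional ablation procedure in the LA, the subject will have to be withdrawn prior to this additional ablation procedure". Section 11.8 repeats the rule beneath its question about LA procedures, "the subject will have to be withdrawn prior to this additional ablation procedure", and adds "Please refer to Section 10.2 for more details".

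**Effect of withdrawal.** Section 10.2 states: "Additional data may no longer be collected after the point at which a subject has been withdrawn from the study". It applies this whatever the reason for withdrawal, and it seeks information on ongoing reportable events only up to that point.

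**Data wanted from the redo.** For an additional ablation "for which a different mapping system was used or different mapping and/or therapeutic catheters were used", Section 11.8 says "detailed information about this additional ablation procedure will be entered in the 'Additional Procedure' eCRF". The items include the operator, whether the LA was treated, whether the index procedure had failed or been left unfinished, the arrhythmia, and the equipment. It continues: "Any reportable adverse event resulting from additional procedures must be captured on the Adverse Event eCRF". No exception is made for withdrawn subjects.

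**Schedule.** The double-asterisk footnote to the data collection schedule (synopsis and Table 11.1-1) limits mapping and procedure data from an additional procedure to LA ablations done with the study devices.

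**The concern.** For LA procedures, the condition that triggers the detailed record in 11.8 (non-study equipment) is also the condition that triggers withdrawal. The site is told to end the subject's participation before the procedure and then to report on the procedure and its complications.

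What is at stake is safety follow-up. The withdrawal is imposed by the protocol rather than chosen by the subject, and it follows an event after the index procedure. Under a literal reading of 10.2, three things go unrecorded:

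- adverse events of the redo;
- late events of the index procedure, or of the month 3 invasive assessment, which Section 8.3 says is not standard of care;
- the month 4 contact, which Section 8.3 says exists to assess subject status and adverse events.

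**Working it through.** No sample size, power or event count enters this point, so the check is a comparison of rules.

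**Step 1: which subjects meet the conflict.**

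| Additional ablation | Withdrawal ordered? | Detailed 11.8 record wanted? | Conflict with 10.2? |
|---|---|---|---|
| LA, study devices | No; it counts as the month 3 assessment if that is still outstanding | Recorded under the month 3 visit in that case | No |
| Outside the LA, other equipment | No | Yes | No |
| LA, other equipment | Yes, before the procedure | Yes | **Yes** |

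The restriction to the LA is explicit in 11.1 and follows from the nesting of the list in 11.8. Only the last row is affected.

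**Step 2: apply the rules to that row.** The subject is withdrawn (11.1, 11.8). The redo takes place. Under 10.2, nothing more may be collected. Under 11.8, the procedure record and any resulting reportable event must be entered. Obeying 10.2 breaks 11.8, and the reverse.

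**Step 3: look for a provision that resolves it.**

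- Section 10.2 allows contact after withdrawal only when withdrawal is due to device safety or performance. It needs the subject's permission and takes place outside the study.
- Section 10.2 also asks that open events be closed or marked chronic. That does not reach a new event from a procedure performed after withdrawal.
- Section 20.1 makes all serious and all procedure-related events reportable, and Table 20.4-1 requires reporting until study end. Section 10.3 has Treatment subjects followed on the full schedule. These add to the tension.
- The schedule footnote leaves out the procedures for which 11.8 wants detail, so it does not match 11.8 either.

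**Step 4: does withdrawal protect an endpoint?** Section 12.2.1 limits the primary analysis to Treatment subjects who complete the month 3 gap assessment. A redo before that assessment with other equipment is a reason to treat the gap endpoint as not evaluable. The withdrawal rule, however, is not confined to the period before month 3. A subject whose gap data are already recorded must still be withdrawn if re-ablated in the LA with other equipment before month 4. Section 10.2 lets data gathered before withdrawal be used, so the primary data survive; only the remaining safety follow-up is given up.

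**Step 5: size.** The documents give no rate of LA redo with non-study equipment. Each affected subject is 1/60 = 1.7% of the treated cohort, and the count could be zero. The follow-up at risk for a redo on day d runs to the month 4 visit. Under 11.1 that visit falls between day 120 − 30 = 90 and day 120 + 30 = 150, so at most 150 − d days are at risk. If the month 3 assessment has been done, 11.10 places month 4 at 30 ± 7 days later, so at most 37 days remain.

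**The case against.** **The case is narrow.** This stands. Only LA redos with other equipment are affected, and redos with the study devices keep the subject in the study.

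**Much of the 11.8 record could be known when the redo is planned.** Operator, reason, arrhythmia and intended equipment could in principle be entered before withdrawal, and a worsening condition that led to the redo would be reportable beforehand. This softens the conflict over the procedure record. It does nothing for adverse events that result from the redo, which cannot be known in advance.

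**No endpoint is touched.** This stands too. Neither the primary endpoint nor the listed secondary ones are safety endpoints, and the primary analysis set already requires a completed month 3 assessment.

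**A stronger reading is tempting.** A reader might infer that the rule strips treatment failures out of the study and so makes reported safety look better than it was. The documents do not support that. The trigger is chamber and equipment, and 11.8 allows for a different arrhythmia. Failures redone with the study devices remain. A definite loss also assumes that 10.2 prevails; a site that follows 11.8 would enter the events. What can be shown is uncertain and possibly inconsistent capture, not a bias of known direction or size.

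**Conclusion.** The contradiction holds for a subject who has an additional LA ablation with a non-study mapping system or catheter, and no other part of the protocol resolves it. The practical consequence is that sites (up to 6, Section 8.1) may handle such subjects differently. Where 10.2 is followed, events from the redo onward and the month 4 status are missing, including for subjects whose gap assessment is complete.

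The number of such subjects cannot be estimated from the documents. The effect is on the completeness of safety reporting, not on the gap endpoint or any listed secondary analysis. The text conflict itself rests on no numerical assumption. It should be corrected, but it does not threaten the study's main result.

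**What to change.** Reconcile Sections 10.2, 11.1 and 11.8 and the schedule footnote (synopsis and Table 11.1-1). In 11.1 and 11.8, replace mandatory withdrawal with wording to this effect:

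*A subject who has an additional LA ablation with a non-study mapping system or catheter is not evaluable for the month 3 gap endpoint if that assessment has not yet been done; data from a completed month 3 assessment are kept. Unless consent is withdrawn, the subject stays in the study for the Additional Procedure eCRF, adverse-event reporting and the month 4 follow-up, timed from the index procedure.*

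Then:

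- remove the pointer from 11.8 to 10.2 for this case, and make clear in 10.2 that loss of evaluability is not withdrawal;
- extend the footnote so that the schedule shows the procedure data 11.8 asks for;
- state that the 11.1 timing of month 4 (120 ± 30 days from index) applies here, because 11.10 counts from a month 3 assessment that may not exist.

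The cost is a few sentences across these sections in a protocol amendment. The eCRF page and the visit already exist. The change concerns data retention only and alters neither treatment nor the choice of equipment.

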11.9. Month 3 Assessment-Ablating physician UNBLINDED to DirectSense technology

Rhythmia HDx + IntellaMap Orion will be used to collect an electroanatomic map (i.e. activation and voltage map) of the Left Atrium. In case gaps are detected and the physician decides to ablate these gaps, ablation must be performed with the IntellaNav MiFi OI catheter.

For all subjects it is preferred that all maps are acquired during pacing from the Coronary Sinus.

Gap sites will be determined for each segment and vein according to **Figure 11.5-2**. The location of each gap will be defined as a site of PV potential on the diagnostic catheter, and in the case of retreatment, to be confirmed by a change in PV activation.

The following DirectSense data has to be collected:

- Blood pool impedance measurements for approximately 10 s. In case the physician decides to ablate, this measurement has to be obtained prior to the 1st RF application (reference measurement)
- Non-ablated myocardium impedance measurements for approximately 10 s prior to the 1st RF application. In case the physician decides to ablate, this measurement has to be obtained prior to the 1st RF application (reference measurement)
- Local impedance data will be sampled approximately every 50 ms. This data will be simultaneously recorded in a digital log file by the BSC representative.

For at least 5 points that are considered as gap-free, the following DirectSense data has to be collected

• Ablated myocardium impedance measurements for approximately 10 s. In case the physician decides to ablate, this measurement has to be obtained prior to the 1st RF application (reference measurement)

For all gaps that are ablated, the following DirectSense data has to be collected:

• Gap impedance measurement for 10 s prior to first ablation within the gap

In case the ablating physician decides to ablate gaps, if any, the ablating physician can use whichever ablation technique he/she prefers. There is also no requirement to perform entrance block testing at the end of the ablation of gaps or to implement a waiting time after the ablation of gaps, if applicable. Also, there is no need to collect a Rhythmia + IntellaMap Orion activation map at the end of the ablation of gaps, if applicable.

11.10. Month 4 Follow Up

Investigators will have to assess subject status at one month (30 days +/-7) after the month 3 assessment. The month 4 follow up has to be performed in-clinic. The data collection at the month 4 follow up includes:

- Visit date;
- Current vital status of subject;
- Reportable Adverse Events, including resolution of ongoing events, if applicable

11.11. Study Completion

Each Treatment subject will be followed until the month 4 follow up. Participation in the study is considered complete upon completion of the month 4 follow up.

In case of premature termination of the study, please refer to Section 23.1.

Following termination/completion of the study, subjects will be managed according to local institution practice.

11.12. Source Documents

Printed, optical or electronic document containing source data shall be used; examples include hospital records, laboratory notes, radiographs, records kept at the investigation site, and/or at the laboratories involved in the clinical study, technical source forms (as defined in section 13.3)

Where copies of the original source document as well as printouts of original electronic source documents are retained, these shall be signed and dated by a member of the investigation center team with a statement that it is a true reproduction of the original source document. If the Principal Investigator delegates this task to one of the investigational team members, the delegation of this task must be documented in the Site Signature and Responsibility Log.

Table 11.12-1: Source Documentation Requirements

Requirement	Disposition
Informed consent documentation process	Retain at Center
Documentation of:	Retain at Center
Signed Technical Source Form for Index procedure and month 3 assessment	Retain at Center

Table 11.12-1: Source Documentation Requirements

Requirement	Disposition	
Rhythmia Advanced Export Case Data	Submit to Boston Scientific	
Printed EP Lab Procedure Report	Retain at Center	
Procedure mapping data (saved to external media, as provided by the sponsor)	Retain at Center	
In the event of patient death (if available):	Submit one copy to Boston Scientific, Retain one copy at center	

12. Statistical Considerations

An overview of the study design, sample size and statistical analysis is provided below.

12.1. Endpoints

12.1.1. Primary Endpoint

The primary endpoint is to assess the association between baseline Local Impedance/Local Impedance drop values per anatomical segment as recorded at index ablation procedure and the proportion of gaps per anatomical segment as measured at the month 3 assessment.

12.1.1.1. Hypotheses

No formal pre-specified statistical hypotheses will be tested in this study.

12.1.1.2. Sample Size

A sample size of 60 subjects is chosen to generate 50 patients with usable data (20% attrition) and have 90% power to detect a minimum difference in DirectSense parameters of 3.71 ohms between segments with and without gaps at month 3.

12.1.1.3. Statistical Methods

While no formal hypothesis test will be performed, 95% confidence intervals for the mean difference in baseline Local Impedance/Local Impedance drop values between segments with and without gaps will used to compare groups.

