	 Undergone any left atrial heart ablation procedure, either surgical or catheter ablation Prosthetic or stenotic valves in the chamber where the intended mapping will occur, or in the path of the catheter access route Subject has a Left Atrial Appendage Closure (LAAC) or Percutaneous Transcatheter Closure of a Patent Foramen Ovale (PFO) Subject has persistent or long-standing persistent atrial fibrillation (AF) (>1 AF episodes lasting greater than 7 days, with no episodes having lasted greater than 30 days, within the past year) Life expectancy ≤ 6 months per physician judgment Subjects who are currently enrolled in another investigational study or registry that would directly interfere with the current study, except when the subject is participating in a mandatory governmental registry, or a purely observational registry with no associated treatments; each instance must be brought to the attention of the sponsor to determine eligibility; The subject is unable or not willing to complete follow-up visits and examination for the duration of the study; Women of childbearing potential who are, or plan to become, pregnant during the time of the study (method of assessment upon physician's discretion). 					
Primary Statistical Hypothesis	No formal pre-specified statistical hypotheses will be tested in this study.					
Statistical Test Method	Descriptive statistics will be used for baseline, procedure and follow-up data collected throughout the study. For the primary endpoint, 95% confidence intervals for the difference of the means will be used to compare DirectSense parameters between segments with and without gaps at month 3.					
Sample Size Parameters	A sample size of 60 subjects is chosen to generate 50 patients with usable data (20% attrition) and have 90% power to detect a minimum difference in DirectSense parameters of 3.71 ohms between segments with and without gaps at month 3.					

ELectrical COupling Information From The Rhythmia TM HDx Mapping System And DireCtSense TM Technology In The Treatment Of Paroxysmal AtriaL FibrIllation- A Non-RandomiZed, ProspEctive Study (LOCALIZE)			
Required Medication Therapy	This study has no specific requirements in terms of medication therapy; the standard of care medication regimen at the investigational site is being followed.		

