The objective of the study is to collect data on the use of the Rhythmia HDx mapping system running commercially available Software Version 2.0 or any future commercially available Software Version with DirectSense technology, the IntellaMap Orion mapping catheter and the IntellaNav MiFi OI ablation catheter, in patients indicated for ablation treatment for denovo PAF. The study will collect specific information to characterize the DirectSense technology in subjects undergoing catheter-based endocardial mapping and ablation for denovo PAF using a commercial Rhythmia HDx mapping system. Direct Sense data will be automatically recorded by the Rhythmia HDx mapping system during ablation procedures. The clinical local impedance data will be analyzed offline and used in order to generate usage guidance on the DirectSense local impedance feature in the management of de-novo PAF cases requiring PVI and in order to further develop a future lesion indexing feature.

7. Study Endpoints

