7.1. Primary Endpoint

Primary endpoint is the association between baseline Local Impedance/Local Impedance drop values per anatomical segment as recorded at index ablation procedure and the proportion of gaps per anatomical segment as measured at the month 3 assessment. Local impedance data will be automatically recorded by the Rhythmia HDx mapping system during PVI for each ablation point. Impedance data will be analyzed offline to determine *Baseline Local Impedance* and *Impedance drops* for each ablation point. For the primary endpoint assessment, impedance data will be grouped per 8 anatomical segments around each PV pair (please refer to **Figure 11.5-2**). Distribution of ablation points and gaps during the index ablation procedure and at the month 3 assessment will be recorded during mapping and ablation with the Rhythmia HDx mapping system.

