A subject who signs informed consent, meets eligibility criteria and had the encircling of the 4 PVs started (post the 1st RF application in the left atrium), but did not have the initial encircling for all 4 PVs (2 PV pairs) completed will be classified as "ATTEMPT". Attempt subjects will be followed up until Pre-Discharge. A subject ID is created by Medidata Rave upon entering the subject in the eCRF. For Attempt subjects, all applicable case report forms must be completed. If applicable, an Adverse Event eCRF form must be completed. Attempt subjects do not count towards the enrollment ceiling and will not be used for analyses of the endpoints. The original signed Informed Consent must be maintained in the center's patient file.

Treatment

A subject who had encircling of the 4 PVs (2 PV pairs) completed will be classified as "TREATMENT". These subjects are followed in accordance with the follow-up schedule and included in all study analyses. A subject ID is created by Medidata Rave upon entering the subject in the eCRF. For Treatment subjects, all applicable case report forms per the protocol must be completed. Treatment subjects do count towards the enrollment ceiling and will be used for analyses of the endpoints. The original signed Informed Consent and any relevant documentation must be maintained in the center's patient file.

It is the investigational sites's responsibility to list all Consent Ineligible, Intent, Attempt and Treatment subjects on the Screening and Enrollment Log.

11. Study Methods

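### The primary 95% CI compares segments, up to 16 of which come from the same patient, and the plan does not say that the interval allows for within-patient correlation

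*Combined protocol and SAP*

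**What the plan says.** Section 12.1.1.3 says that groups will be compared by "95% confidence intervals for the mean difference in baseline Local Impedance/Local Impedance drop values between segments with and without gaps". The synopsis, under Statistical Test Method, gives the same plan in slightly different words: "95% confidence intervals for the difference of the means will be used to compare DirectSense parameters between segments with and without gaps at month 3". Neither place names an interval formula or a variance estimator.

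Section 7.1 fixes the grouping: "impedance data will be grouped per 8 anatomical segments around each PV pair". Section 10.3 gives the number of pairs: "A subject who had encircling of the 4 PVs (2 PV pairs) completed will be classified as" Treatment. Under Section 12.2.1 the primary analysis set is the Treatment subjects who complete the month 3 gap assessment, and Section 12.1.1.2 plans for 50 patients with usable data.

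Section 12.1.1.1 states: "No formal pre-specified statistical hypotheses will be tested in this study". Section 12 introduces itself as a summary: "An overview of the study design, sample size and statistical analysis is provided below". It points to no further analysis plan, and Section 12.3.2 treats the analyses in the protocol as the planned ones, with changes to be explained in the study report.

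**The concern.** The segments of one patient share one heart and one index procedure, usually with one operator. Impedance readings and gaps could each be more alike within a patient than between patients. If both are, 800 segments carry less information about the difference than 800 independent segments would, and an ordinary two-sample interval is too narrow.

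This interval is the only stated primary inference, and by Section 6 the impedance data will be "used in order to generate usage guidance on the DirectSense local impedance feature". No hypothesis is tested, so no type I error claim is at stake. The possible harm is an interval labelled 95% that does not have 95% coverage. A second cost is that two analysts following Section 12.1.1.3 could report different intervals from the same data.

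**Working it through.** **Inputs from the documents.** Segments per PV pair: 8 (Section 7.1). Pairs per Treatment subject: 2 (Section 10.3). Usable patients: 50 (Section 12.1.1.2). So 8 × 2 = 16 segments per patient and 50 × 16 = 800 segments. Both are maxima. An untargeted segment is only a protocol deviation (Section 11.5.2.1). The figure of 16 also rests on the endpoint wording, which counts per PV pair, whereas the caption of Figure 11.5-2 and the gap-closure text count per PV.

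**Search for a provision.** No section names a clustered variance, mixed model, GEE, bootstrap, patient-level summary or ICC. Where the text speaks of correlation, it means impedance against gaps. The limit of 30 procedures per site (Sections 8.1 and 12.2.3) concerns centers. Section 12.2.2, on bias, concerns patient selection.

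**The plan's own figure.** The 90% power for 3.71 ohms cannot be reproduced, because no SD or gap rate is given. On 800 independent segments with 10% gaps (80 against 720) and two-sided 5%, the implied SD is 3.71 / [(1.960 + 1.282) × √(1/80 + 1/720)] = 9.71 ohms. At 5% and 20% gaps it is 7.06 and 12.95. A paired calculation on 50 patients implies an SD of differences of 8.09. The text does not show which was used.

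**Assumptions for the rest (none in the documents).** SD 10 ohms, 10% gaps unless stated, 50 patients × 16 segments, no true association, and the ICCs shown.

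**Coverage of the two-sample interval.** DE = 1 + (16 − 1) × ICC(impedance) × ICC(gap). Approximate coverage = 2Φ(1.96/√DE) − 1.

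| ICC impedance / gap | DE | Coverage, formula | Coverage, simulated |
|---|---|---|---|
| 0.3 / 0 | 1.00 | 95.0% | 95% |
| 0.1 / 0.1 | 1.15 | 93.2% | 93–94% |
| 0.2 / 0.2 | 1.60 | 87.9% | 87–88% |
| 0.4 / 0.1 | 1.60 | 87.9% | 88–89% |
| 0.5 / 0.1 | 1.75 | 86.2% | 87% |
| 0.3 / 0.2 | 1.90 | 84.5% | 84–85% |
| 0.5 / 0.3 | 3.25 | 72.3% | 72–74% |

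The product of the two ICCs drives the loss, so neither ICC has to reach a threshold of its own.

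**Gaps spread evenly.** With exactly 2 gaps in every patient (12.5%) and impedance ICC 0.3, the two-sample SE is 10√(1/100 + 1/700) = 1.07 ohms. The patient effect cancels, so the true SE is 1.07 × √0.7 = 0.89. Coverage is 2Φ(1.96/√0.7) − 1 = 98%, and the interval is too wide.

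**Patient-clustered interval for the same difference.** With a CR2 variance and Satterthwaite degrees of freedom, simulated coverage was about 94–96% in every setting tried. The ordinary sandwich with 49 df fell to about 88–91% at 5% gaps with the larger ICCs, which is why a small-sample correction matters. At ICCs 0.3/0.2 and 10% gaps, the two-sample SE is 10√(1/80 + 1/720) = 1.18 ohms and the mean clustered SE is about 1.5–1.6.

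**Unadjusted difference against a random-intercept model.** Suppose low-impedance patients have more gaps but there is no association within patients (gap log-odds falling 0.8 per SD of the patient effect, impedance ICC 0.3). The unadjusted difference then averages about −4.0 ohms and the random-intercept coefficient about −0.6. The two methods answer different questions.

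**The case against.** The best defense is that the text is silent and not wrong. A clustered interval satisfies Section 12.1.1.3 as written. So might a paired within-patient contrast, since that section speaks of a mean difference and Section 12.1.1.2 sizes the study in patients. The study is a descriptive post-market study with no hypothesis test, and Section 12 is offered as an overview. All of this is fair, and it limits the finding to an unspecified method. It does not remove it: the synopsis wording fits a paired reading less well, no further plan is referred to, and the plain reading is a two-sample interval.

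The second defense is that the size rests wholly on assumed ICCs. That stands. A reader might infer that the primary interval will be too narrow, or that the 90% power is overstated. The documents support neither. Without an ICC, SD or gap rate the direction is unknown, and the unit behind the power figure is not given. The lowest coverages in the table need ICCs for which the documents offer no evidence.

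A reader might also infer that the unadjusted segment difference must be the target and that a mixed model would be an error. The documents choose neither. For segment-level guidance a within-patient contrast may be the more useful quantity, because a clustered interval gives honest error bars around a between-patient difference but does not remove it. Clustering on patient also leaves any operator or site correlation unaddressed.

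**Conclusion.** The concern holds as an unspecified method with a conditional consequence, and it should be fixed. It is certain that the comparison is between segments, that a patient can supply up to 16 of them, and that no allowance for within-patient correlation is stated. What follows depends on quantities the documents do not give. A two-sample interval loses little at ICCs of 0.1/0.1 (about 94% coverage) and materially more at 0.2/0.2 or 0.4/0.1 (about 88%) or 0.3/0.2 (about 84%). It is about right if gaps do not cluster, and too wide if gaps are spread evenly. These figures assume 50 × 16 segments, SD 10 ohms, about 10% gaps and no true association.

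**What to change.** In Section 12.1.1.3 and in the synopsis, state that the segment is the unit of analysis. State also that the 95% CI for the mean difference, for baseline local impedance and for impedance drop, uses a method that accounts for clustering by patient. One suitable choice is a patient-clustered variance with a small-sample correction, such as CR2 with Satterthwaite degrees of freedom, because gaps may be few. If a patient random-intercept model is used instead or as well, say that it estimates a mainly within-patient contrast, which can differ from the unadjusted difference.

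The cost is a few sentences and minor programming, with no new data. The interval may become wider if gaps cluster (SE about 1.5–1.6 against 1.2 ohms at ICCs 0.3/0.2, 10% gaps, SD 10, all assumed). It may become narrower if gaps are evenly spread (0.89 against 1.07 ohms in the example above).
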